I agree to promptly report to the applicable ethics boards any changes in the research activity and all unanticipated problems involving risks to human participants or others. Additionally, I will not make any changes in the research without prior ethics and sponsor approval, except where necessary to ensure the safety of study participants.

Schematic of Study Design

- ✓ Biological female aged 40- 60
- ✓ Documented HIV-1 infection
- ✓ Peri-menopausal or within 10 years of menopause
- ✓ Signed informed consent form and willing to comply with protocol
- ✓ cART regimen containing ritonavir boosted PI or NNRTI or an II in combination with TDF-FTC for > 24 weeks
- ✓ Stable viral suppression (HIV-RNA <50 copies/ml) for > 24 weeks
- ✓ If of childbearing potential, using effective birth control methods and willing to continue during trial
- ✓ Assessed for vitamin D and calcium dietary intake; if inadequate for age, supplements recommended
- ✗ HIV-2
- ✗ High 10-yr fracture risk at baseline
- ✗ Current treatment with active bone medications
- ✗ Current use of systematic steroids
- ✗ Acute viral hepatitis
- ✗ Chronic HCV or expected to require HCV treatment during trial period
- ✗ Any investigational ARV within 30 days
- ✗ Dialysis or renal insufficiency
- ✗ History of decompensated liver disease or presence of ascites, encephalopathy, coagulopathy, hypoalbuminemia, esophageal or gastric varices
- ✗ Pregnant or breastfeeding
- ✗ Screening blood result with any grade 3/4

Primary Endpoint: Comparison of % change from baseline in BMD at spine at week 48

ABBREVIATIONS AND DEFINITIONS

Acronym / Abbreviation	Definition
AE	Adverse Event
ARV	Antiretroviral
BMD	Bone Mineral Density
CaMos	Canadian Multicentre Osteoporosis Study
cART	Combination antiretroviral therapy
DAIDS	Division of Aids (table for grading severity of adverse events)
DXA	Dual Energy X-ray Absorptiometry
F/TAF or TAF/FTC	Tenofovir alafenamide – coformulated with Emtricitabine
FTC	Emtricitabine
FRAX®	Algorithm for calculating fracture risk
HATS	HIV Adherence Treatment Scale
HCV	Hepatitis C virus
HIV	Human immunodeficiency virus
HRpQCT	High-resolution peripheral quantitative computed tomography
IATA	International Air Transportation Association
ICJME	International Committee of Medical Journal Editors
NNRTI	Non-nucleoside reverse transcriptase inhibitor
PI	Protease Inhibitor
RCT	Randomized Controlled Trial
SAE	Serious Adverse Event
SPPB	Short performance physical battery
TAF	Tenofovir alafenamide

1.0 BACKGROUND AND SCIENTIFIC RATIONALE

1.1 Introduction

With health advances from combination antiretroviral therapy (cART) management of comorbid illness is now a major focus of research and clinical care of HIV infected persons.^{1,2}

Osteoporosis is a systemic skeletal disease with an increase in bone fragility and susceptibility to fracture³. HIV independently contributes to low bone mineral density (BMD) through viral, immune, inflammatory and ART-related effects on bone metabolism.^{4,5}

The Canadian Multicentre Osteoporosis Study (CaMos) estimates the prevalence of osteoporosis at the lumbar spine in the general population of women > age 50 to be 12.1%.⁶ The most serious manifestation is a fragility fracture, defined as a fracture occurring spontaneously or following minor trauma. The consequences of fracture include increased mortality, morbidity, institutionalization and economic costs. There is a 25% risk of death in the year following a hip fracture with excess risk continuing into the second year.⁷ The HIV population is aging with > 50% now over 50 years. Osteoporosis is higher in HIV relative to the general population, is greater in severity and increases with age.^{8,9}

Although greater BMD losses are seen with initiation of cART including tenofovir (TDF) relative to other antiretroviral agents¹⁰⁻², the co-formulation of TDF/FTC (emtricitabine) is the preferred NRTI backbone for most cART regimens and hence the majority of HIV patients are exposed to TDF, often for many years.¹³ Greater BMD losses are seen when cART is initiated with this agent, possibly due to a form of immune reconstitution syndrome¹⁴. Further BMD loss occurs with continued use likely due to an effect on osteoclastic activity¹⁰. Cohort studies have observed an increased fracture risk with use of this agent especially with age.^{15,16} The relative importance of low BMD to clinical care differs significantly between countries and regions, based on factors such as the population at risk, access to adequate screening resources and physicians' knowledge.¹⁷ There are no guidelines as to whether BMD should be monitored differently in HIV than the general population, whether HIV alone is an independent factor to be used in fracture risk assessment nor whether TDF should be discontinued if osteoporosis develops on therapy.¹⁰ In many situations, it is not safe to stop TDF for risk of loss of HIV control.

1.2 Study agent

As a prodrug, tenofovir disoproxil fumarate is initially metabolised to tenofovir, which is subsequently metabolised in cells to tenofovir-diphosphate. Although intracellular tenofovir-diphosphate is responsible for the drug's antiviral activity, higher circulating plasma levels of tenofovir have been associated with an increased risk of both renal and bone toxicity. A novel tenofovir prodrug tenofovir alafenamide results in roughly four times higher intracellular concentrations of the active metabolite tenofovir-diphosphate compared with tenofovir disoproxil fumarate, allowing for much lower doses of tenofovir alafenamide versus tenofovir disoproxil fumarate. Because of tenofovir alafenamide's reduced dose and the improved stability,

plasma exposure of tenofovir is 90% lower with tenofovir alafenamide than with tenofovir disoproxil fumarate, which is believed to reduce the risk of renal and bone toxicity.¹⁸ Initial licencing studies compared a co-formulation of TDF/FTC with an integrase inhibitor elvitegravir boosted by cobicistat (Stribild) to a similar co-formulation of elvitegravir, cobicistat and TAF/FTC¹⁹. The non -inferior viral suppression rates, CD4 count increases, rate and spectrum of adverse events, and resistance profiles with failure led to the approval of the latter as Genvoya²⁰, recently in use in Canada. Of note, Initiation of cART with TAF/FTC was shown to cause statistically significant lesser BMD losses, and smaller declines in glomerular renal function than TDF/FTC¹⁹. The lower serum level is thought the reason for potential less bone and renal toxicity.

Subsequent studies that evaluated a switch from TDF/FTC to TAF/FTC in HIV infected persons with viral suppression, the absence of viral resistance and with a variety of third cART agents were associated with a small but statistically significant increase in BMD²¹⁻³ in largely younger male populations. Although BMD assessment with dual energy x-ray absorptiometry (DXA) is well established for the diagnosis of osteoporosis and for fracture risk assessment in postmenopausal women it is not validated in young men.¹⁴ Therefore it remains uncertain whether these changes will be clinically relevant.

1.3 Rationale for this Study

TAF (co-formulated with FTC) as a fixed tablet regimen is recently licenced in Canada²⁴ and Europe. It will be unclear for treating physicians and policy makers whether all HIV+ who require TDF/FTC should be switched to TAF/FTC. It is anticipated that the cost will be similar to the current price for TDF/FTC (approximately \$1000 CAN per month), however generic TDF/FTC will soon be available and will be considerably cheaper. Statistically significant increases in BMD that are not linked to clinical outcomes will be insufficient to guide that decision.

Given sample size considerations and time to fracture endpoints, clinical validation studies are not possible. Further, it is unknown whether BMD can be improved in aging HIV+ women through cART switching. Demonstrating changes in BMD that correlate with fracture risk in a population of older HIV infected women in whom BMD data is validated with fracture risk will provide better evidence. To better understand the potential impact, in this study we also include new bone imaging modalities – trabecular bone score²⁵ and HR-pQCT²⁶ that collect further information about bone microarchitecture and bone strength to more fully understand changes in bone health. There is emerging evidence that changes detected by these new imaging modalities are independently associated with fracture risk. In previous work we showed an excess of fragility fractures in HIV infected women despite similar BMD scores.²⁷ suggesting that other parameters are important to evaluate risk. Since women experience sharp declines in BMD during menopause, the potential for improved bone health through adjustment of HIV therapy may reduce future health burdens associated with osteoporosis

1.4 Potential risks and benefits to participants

Tenofovir alafenamide as an individual agent has been administered to more than 40 HIV-positive participants in two separate studies. In study GS-US-120-1101, participants received higher doses of TAF (50 mg and 150 mg) than the TAF dose in this study. Side effects that were seen in more than two participants were headache, nausea, and gas (flatulence). In study GS-US-120-0104, adverse events observed in more than two participants were nausea and fatigue. One serious adverse event of chest pain was reported, but not considered related to study drugs.²⁸

In addition, F/TAF has been given to over 3000 HIV infected participants in switching studies²¹⁻³. In these trials, there was no new toxicity observed relative to TDF/FTC and less than 1 % had to discontinue medication secondary to adverse events. The most frequently described adverse events occurring in more than 5% of persons included headache, diarrhea, nasal congestion, and fatigue.

A study in dogs detected eye problems (posterior uveitis- inflammation in the back of the eye) in some dogs when TAF was given at the highest doses. There have not been cases of uveitis related to TAF in clinical studies.²⁸

TAF is a drug similar to Tenofovir disoproxil fumarate (TDF), Viread®, an approved medication by the FDA for the treatment of HIV and hepatitis B infection²⁹. The side effects for TAF are expected to be similar to Viread®. The side effects for Viread® are listed below.

Tenofovir DF (TDF, Viread®)

Tenofovir DF has been studied in more than 12,000 HIV-infected adults for as long as 480 weeks in some patients. Common potential side effects identified in patients who received at least one dose of tenofovir DF 300 mg include diarrhea, nausea, vomiting, flatulence (intestinal gas), and dizziness. Those side effects were often mild or moderate in severity, and did not lead to discontinuation of tenofovir DF.²⁹

In addition to side effects reported from clinical trials the following side effects have also been identified after tenofovir DF was approved by the FDA and Health Canada in HIV-infected patients treated with combination therapy that has included tenofovir DF and other anti-HIV drugs. Because post marketing (after regulatory licensing) reactions are reported voluntarily from a patient population of uncertain size, it is not always possible to reliably estimate how frequently these side effects occurred, or establish a causal relationship to tenofovir DF. The side effects which have been reported with tenofovir DF when taken with other anti-HIV drugs include:

- allergic reaction
- rash
- abdominal pain
- pancreatitis
- shortness of breath
- weakness
- abnormalities of hepatic (liver) function and hepatitis (inflammation of liver).

Cases of lactic acidosis, hepatosteatosis, including fatal cases, were reported in HIV-infected patients treated with anti-retroviral agents similar to tenofovir DF. The symptoms of lactic acidosis include:

- weakness
- unexpected and uncommon abdominal pain
- nausea
- vomiting

Symptoms of liver problems include:

- yellowing of the skin or whites of the eyes
- dark urine
- light colored bowel movements
- nausea
- loss of appetite
- lower abdominal pain

Cases of kidney damage have been reported in patients taking tenofovir DF who already have atherosclerosis, or specific kidney disease, and patients who, while receiving tenofovir DF, were also taking medications that may cause damage to the kidneys. Kidney damage has also been reported in patients without any of these factors. In addition, continuous or sudden kidney failure, abnormal kidney function, inflammation of the kidneys, protein in the urine, excessive urination, nephrogenic diabetes insipidus, and increased creatinine have also been reported in patients taking tenofovir DF.

Bone toxicity, including a decrease in bone mineral density was seen in animals following treatment with tenofovir DF. Decreases in bone mineral density have been seen in humans. The risk of bone fractures associated with these types of changes is unknown.

Because these events have been reported voluntarily from a population of unknown size, estimates of frequency cannot be made.

Emtricitabine (FTC, Emtriva®)³⁰

The most common adverse reactions seen in greater than or equal to 10% of patients treated with FTC include:

- headache
- diarrhea
- nausea
- fatigue
- dizziness
- depression
- trouble sleeping
- abnormal dreams
- rash
- abdominal pain
- weakness
- increased cough
- runny nose

Other common side effects seen more than 1% and less than 10% with emtricitabine include: pain, weakness, vomiting, indigestion, changes in skin color primarily on the palms and/or soles, increased triglycerides, increased bilirubin, increased blood glucose, allergic reaction, increased liver enzymes, increased pancreatic enzymes and low white blood cell count.

Rare cases of lactic acidosis, and hepatosteatosis were reported in HIV-infected patients treated with anti-HIV medications similar to emtricitabine.

Allergic Reaction Risks

As with taking any drug, there is a risk of allergic reaction.

Blood Draws

Drawing blood from a vein may cause local pain, bruising, occasional light-headedness, fainting, and very rarely, infection at the site of the blood draw.

DXA

Decreases in bone mineral density have been observed in HIV-infected patients¹⁰. An X-Ray called dual energy X-ray absorptiometry, or a DXA scan, will be performed on spine and hip to measure changes in bone mineral density. The radiation exposure is lower than with a chest x-ray. The DXA scans are considered, in general, less harmful than a standard x-ray³¹

HRpQCT

This scan provides different types of information about bone strength and structure. Measurements are done on one forearm and one ankle and are performed when seated in a chair. This exposes participants to a small amount of radiation similar to that of the DXA scan³¹. This test will only be available at selected participating sites.

Hepatitis B and C Testing Risks

Participants will be tested for Hepatitis C and B at the screening visit, if not previously recorded. The results of these tests, if active, must be reported to the local health authority, such as Public Health.

2.0 STUDY SYNOPSIS

This is a randomized controlled clinical trial (RCT) of immediate vs delayed switch from TDF/FTC to TAF/FTC to define the impact of switching ARV on BMD in different stages of the aging trajectory in HIV infected women. Included is a geriatric assessment based on the conceptualization of health transition across menopause. The study will be conducted in five Canadian (University Health Network, Vancouver Infectious Diseases Centre, Centre Hospitalier de l'Université Laval, McGill University Health Centre, Hamilton Health Sciences Centre, and two Italian centres (Modena metabolic clinic and Milan clinic) by HIV physicians with interest and expertise in women's issues in HIV care. The Maple Leaf medical clinic in Toronto will refer all their participants to the UHN site for study procedures.

3.0 STUDY HYPOTHESIS

The primary hypothesis is that switching from TDF/FTC will improve BMD to a degree that correlates with a lower fracture risk in aging HIV+ women. We will further explore our theory that the impact is greater in those in the early stages of menopause and in those who also receive a protease inhibitor (PI) as the third ARV.

4.0 STUDY OBJECTIVES

4.1 Primary objectives:

To determine if:

1. Switching HIV+ women on TDF/FTC to TAF/FTC increases BMD at the spine at 48 weeks relative to those who continue TDF/FTC
2. To determine if any observed improvements continue or stabilize in the year after switch.

4.2. Hypothesis generating objectives:

To determine if the effect of switching from TDF/FTC to TAF/FTC on BMD varies by stage of menopause and by third ARV.

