5.5 Secondary endpoints

We will compare changes between the immediate and delayed group from data collected at screening or baseline and weeks 48 and 96.

% change from baseline in BMD at lumbar spine at 96 weeks

% change from baseline in BMD at hip at 48 weeks

% change from baseline in BMD at hip at 96 weeks

Changes in Bone architecture as determined by Trabecular bone scan (TBS)²⁵ and HRpQCT²⁶

Changes in 10 year fracture risk determined by country specific FRAX calculator³³

% with undetectable viral load HIV-1 RNA as per current assays. (This **may be** < 50/ml, < 40/ml or viral load not detected)

Change from baseline in geriatric functional measures: frailty, performance and balance

Change from baseline in muscle quality: Sarcopenia – grip strength measured by a Dynamometer and fat free mass measure (from the DXA)

Change from baseline in lipid values and Framingham cardiovascular risk scores

Changes in renal tubular and glomerular function: eGFR, Cr, urine alb/cr and protein/cr, glucosuria

Safety (clinical and laboratory adverse events)

Changes in biomarkers of inflammation, coagulation and bone metabolism

Tolerability (EuroQoL questionnaire)

5.6 Justification of Endpoints:

Primary Endpoint: BMD assessment with dual energy x-ray absorptiometry (DXA) is well established for the diagnosis of osteoporosis and for fracture risk assessment in postmenopausal women⁷. For BMD measurements to be clinically useful, they are expressed in comparison with

established normative databases. BMD is expressed as a numerical value (g/cm²). Change in BMD is considered a valid intermediate end point for efficacy of fracture risk reduction⁷. To inform the site and timing of the primary endpoint, data from studies of bisphosphonates (a major therapy for osteoporosis) was used in which the increase in BMD is greatest at the lumbar spine, with one half of the gain of BMD achieved within 6–12 months followed by a lower increase over subsequent years³⁴

Secondary Endpoints: New imaging modalities are increasingly incorporated into studies of osteoporosis to gain more detailed information on bone strength.

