8.3 Follow-up Visits for Participants

These will occur at weeks 4, 12, 24, 36, 48, 52, 60, 72, 84 and 96. At weeks 4, 12, 24, 36, 52, 60, 72, and 84, the participants will have routine investigations as per the study site, and will complete targeted physical exams. **Complete** physical exams, labwork as outlined in the schedule of Assessments on pages 25 – 26, and FSH (if premenopausal) will be required at weeks 48 and 96. Adverse events will be captured at each study visit as will any changes in clinical conditions or medications. Pill counts of returned study drug except week 52 will also be captured. The accepted windows around study visits are +/- 7 days. The procedures will last about 60 minutes.

If they agree, participants will continue to be followed even if they decide to stop the study medication

At weeks 48 and 96 all participants will complete the study imaging, collection of plasma specimens for marker banking, quality of life questionnaires, FRAX score as determined by country specific FRAX calculator, Framingham cardiovascular risk score, and geriatric measures as above. The additional procedures will last

approximately 30 minutes plus imaging time. The imaging is to be scheduled within 4 weeks of these visit dates.

Drug dispensation will be done every 3 months during the regular visits at W0, 12, W24, W36, W48, W60, W72, and 84. At week 48, all participants will receive open label TAF/FTC.

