11. ASSESSMENT OF SAFETY

11.1 Adverse Events (AEs)

Adverse events (AEs) are defined as any untoward medical occurrence in a participant that does not necessarily have a causal relationship with the study medication/intervention. An AE can therefore be any unfavourable and unintended sign (including abnormal laboratory finding), symptom, or disease temporally associated with the use of study drug/intervention, whether or not it is related to the medication/intervention.

Toxicities will be graded on a 4-point scale according to standard guidelines outlined in the “Division of AIDS Table for Grading the Severity of Adult and Pediatric Adverse Events”⁴⁸[Appendix C]. In general, grade 1 and 2 events will not be considered adverse events, but details should be documented in the source documents. Fractures will be considered and captured as an adverse event regardless of grading.

Stable chronic conditions which are present prior to clinical study entry and do not worsen are not considered adverse events and will be accounted for in the participant's medical history.

Participants who have an adverse event should be followed and treated by the site Investigator until the abnormal parameter or symptom has resolved or stabilized. It is up to the clinician to determine that the AE is either resolved or that it has reached a stable state, after which no further follow-up is necessary. There should also be source documentation to support this determination.

Rates of adverse events, serious adverse events and hospitalisations will be compared between the two arms. Specific attention will be paid to HIV RNA (see below), CD4 cell counts, and metabolic parameters such as fasting glucose, and lipid profiles.

The most common adverse reactions of moderate to severe intensity and incidence $\geq 2\%$ in those receiving TAF are headache, fatigue, nasal congestion and diarrhea.

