In the GLMM model of percent change in BMD at the spine, each patient shall contribute two data points: the percent change in BMD at the spine at 48 weeks and the percent change in BMD at the spine at 96 weeks. A variogram will be used to determine the amount of error due to random effects and serial correlation. If random effects are the source of a significant amount of variation, terms for random intercept and random time shall be included in the model. If serial correlation is determined to be the main source of error, a single parameter will be required to model the correlation between the week 48 and week 96 values from a single patient, since there will be only two BMD values per patient after enrolment.

The model shall contain four covariates: (1) treatment arm, (2) a binary indicator for whether or not the data point corresponds to week 96, (3) the interaction between the treatment arm and the 96 week indicator and (4) a binary for country (Canada vs Italy). If sufficient woman are receiving hormone replacement therapy, an additional binary covariate may be included to capture whether or not the woman was receiving hormone replacement therapy at randomization.

The GLMM model can be expressed as follows:

$$Y = \beta_0 + \beta_1 \text{ treatment} + \beta_2 \text{ week 96} + \beta_3 \text{ treatment* week 96} \quad (1)$$

where Y is the percent change in BMD at the spine.

The hypothesis test for the primary analysis is $H_0: \beta_1 = 0$, which corresponds to the primary hypothesis of the effect of switching from TDF to TAF on percent change in BMD at the spine at 48 weeks.

13.3 Secondary analyses:

The secondary endpoints of greatest importance are: the percent change in BMD at the hip at week 48, the percent change in BMD at the hip at week 96, and the percentage change at the spine at week 96. GLMM will be used to estimate the effect of immediate switch to TAF/FTC on these outcomes

The hypothesis test for the secondary analysis is $H_0: \beta_3 = 0$ in model (1) above, which corresponds to the secondary hypothesis of the effect of switching from TDF to TAF on percent change in BMD at the spine at 96 weeks.

A similar model will be fit for the outcome of percent change in the spine. In that model, the hypothesis tests of $H_0: \beta_1 = 0$ and $H_0: \beta_3 = 0$ will both be of interest, corresponding to the secondary hypotheses of the effects of switching from TDF to TAF on percent change in BMD at the hip at 48 and 96 weeks, respectively.

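### Primary objective 2 (does the gain continue or stabilise?) is answered neither by the week-96 arm comparison nor by the test of β3, which is mislabelled as the effect of switching at 96 weeks

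*Combined protocol and SAP*

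**What the plan says.** Section 4.1 gives two primary objectives. The second is "To determine if any observed improvements continue or stabilize in the year after switch".

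Section 5.5 lists no endpoint for change between weeks 48 and 96. Its introduction reads "We will compare changes between the immediate and delayed group from data collected at screening or baseline and weeks 48 and 96", and the nearest item is the percent "change from baseline in BMD at lumbar spine at 96 weeks", with a hip counterpart. Both are secondary.

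Section 8.3 states: "At week 48, all participants will receive open label TAF/FTC". Section 9.0 agrees.

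Model (1) in Section 13.2 has terms for treatment arm, a week-96 indicator and "the interaction between the treatment arm and the 96 week indicator", whose coefficient is β3. Section 13.3 tests β3 = 0 and says that this corresponds to "the secondary hypothesis of the effect of switching from TDF to TAF on percent change in BMD at the spine at 96 weeks". It gives the hip β3 the same meaning.

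On safety, Section 11.1 says "Rates of adverse events, serious adverse events and hospitalisations will be compared between the two arms" and names no period. Sections 11.3 and 11.5 run adverse event surveillance to 30 days after week 96.

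**The concern.** Whether an improvement continues or stabilises is a question about the course of BMD after the first year on TAF/FTC. DXA is done only before baseline and at weeks 48 and 96 (Section 8.7). The one place to see the answer is therefore the change from week 48 to week 96 in women who switched at week 0. No endpoint or test names that change, and no criterion for continuing or stabilising is given.

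The plan instead has a between-arm comparison made when no TDF arm exists, and a test whose stated meaning does not match its coefficient. If the analysis follows Section 13.3 literally, a lasting benefit could be reported as a harmful effect of switching at 96 weeks, and a lasting gain could not be told from a lost one.

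**Working it through.** **Inputs from the documents.** 64 women per arm, difference 1%, SD 2%, 80% power, significance level .05 (Section 13.1). 10% dropout before week 48 (Section 13.7). One cited switch study with +1.5% on TAF and −0.2% on TDF at 48 weeks (Section 13.1).

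**Assumptions.** Two-sided tests; SD 2% at week 96 as well; normal approximation; correlation ρ between the week-48 and week-96 values of 0.5 to 0.9 (the documents give none); treatment coded 1 for immediate and 0 for delayed. The scenario means are illustrative.

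**Step 1: the plan's own figure.** n per arm = 2 × (1.96 + 0.842)² × 2² / 1² = 62.8, so 63 by the normal formula. The t test named in the plan needs 63.8, so 64 (power 80.1%). The figure reproduces and is not at issue.

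**Step 2: what model (1) estimates.** The country covariate is additive and cancels from every contrast.

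| Mean percent change | Week 48 | Week 96 |
|---|---|---|
| Delayed | β0 | β0+β2 |
| Immediate | β0+β1 | β0+β1+β2+β3 |

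- Arm difference at week 48: β1 (TAF versus TDF)
- Arm difference at week 96: β1+β3 (96 versus 48 weeks of TAF/FTC)
- Delayed arm, week 48 to 96: β2
- Immediate arm, week 48 to 96: β2+β3
- β3 alone: (β1+β3) − β1, the change in the arm difference

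**Step 3: scenarios.** Entries are percent change from baseline at weeks 48 and 96.

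| Scenario | Immediate | Delayed | β1 | β1+β3 | β3 | β2+β3 |
|---|---|---|---|---|---|---|
| A. Gain kept, delayed arm fully catches up | +0.5, +0.5 | −0.5, +0.5 | 1.0 | 0 | −1.0 | 0 |
| B. Gain kept, delayed arm half catches up | +0.5, +0.5 | −0.5, 0 | 1.0 | 0.5 | −0.5 | 0 |
| C. Cited-study figures, gain kept, delayed arm gains 1.5 | +1.5, +1.5 | −0.2, +1.3 | 1.7 | 0.2 | −1.5 | 0 |
| D. TAF only halts loss | 0, 0 | −1, −1 | 1.0 | 1.0 | 0 | 0 |
| E. Gain continues, arms move in parallel | +0.5, +1.0 | −0.5, 0 | 1.0 | 1.0 | 0 | +0.5 |
| F. Gain lost, delayed arm gains nothing | +0.5, −0.5 | −0.5, −0.5 | 1.0 | 0 | −1.0 | −1.0 |

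A and F are opposite answers to objective 2, yet they agree on both planned contrasts. D and E also agree on both, although the level holds in one and rises in the other. β2+β3 separates each pair.

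**Step 4: how often the tests reject.** SE of β1+β3 = 2 × √(2/64) = 0.354. SE of β3 = 2 × √(2(1−ρ)) × √(2/64) = 0.354, 0.274 and 0.158 at ρ = 0.5, 0.7 and 0.9.

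- A: the week-96 difference is rejected 5% of the time. β3 is rejected 81%, 95.5% and over 99%, with a negative sign.
- B: the week-96 difference 29%; β3 29%, 45% and 88.5%.
- C: the week-96 difference about 9%; β3 about 99% or more.
- D and E: the week-96 difference 81%; β3 5%.

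With 10% dropout (64 × 0.9 = 57.6 per arm), β3 in A is rejected 76.5%, 93.4% and over 99%.

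**Step 5: precision of the contrast that answers objective 2.** SE of β2+β3 = 2 × √(2(1−ρ)/64) = 0.25, 0.194 and 0.112. The 95% CI half-width is 0.49, 0.38 and 0.22 percentage points, or 0.52, 0.40 and 0.23 with 10% dropout.

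**Step 6: safety period.** If all 96 weeks were pooled, 48/96, or half, of the delayed arm's follow-up would be on TAF/FTC.

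**The case against.** The delayed switch is deliberate, Section 5.4 names one primary endpoint at week 48, and the week-96 outcomes are secondary. Model (1) already contains β2+β3, so the data and the model can answer objective 2. Section 13.3 also describes its models as estimating the effect of immediate switch, so the TDF-to-TAF label is not used throughout. The phrase about the year after switch is itself ambiguous: read literally, it is weeks 0-48 in the immediate arm and 48-96 in the delayed arm. Finally, β2+β3 is uncontrolled, and the loss of 1-3% per year expected in Section 13.1 is at least as large as the 1% target effect.

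All of this stands. It limits the point to an unnamed contrast and a wrong interpretation. It does not rescue the stated test, because nothing in the plan says that β2+β3 will be estimated or used for objective 2.

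Three stronger readings are tempting and are not supported:

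- A reader might infer that a maintained gain would be reported as no effect. That can hold for the week-96 arm difference under full catch-up, but Section 13.3 tests β3, which is then negative. If TAF only halts loss, the arm difference stays at 1.0.
- A reader might extend the mislabelling to the week-96 renal and lipid results. Section 13.3 says that other secondary endpoints, with eGFR as an example, are summarised and not formally compared.
- A reader might infer that adverse events will be pooled over 96 weeks and the contrast diluted. Section 11.1 gives no period, and start dates are recorded (Section 11.2), so a week 0-48 comparison is available. The period is unspecified; dilution is not established.

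**Conclusion.** The point holds as an error of interpretation and a missing estimate. A primary objective has no named estimate that answers it, and the test offered at week 96 carries a meaning that its coefficient does not have. That β3 is not the week-96 effect follows from model (1) and needs no assumption about the data.

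The size depends on the delayed arm. With a 1% gain kept and full catch-up, β3 is −1%, rejected about 81% of the time at an assumed correlation of 0.5 and more often at higher ones. With half catch-up it is −0.5%, and with no catch-up it is 0. The inability to tell a kept gain from a lost one is shown by scenarios A and F, which are possible patterns and not forecasts.

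The week-48 primary endpoint, the β1 test and the sample size are not affected.

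**What to change.** 1. State in Sections 4.1, 5.5 and 13 that objective 2 is estimated by β2+β3, the immediate arm's change in spine BMD from week 48 to week 96, with a 95% CI. Define which period the year after switch means. Say that the estimate is within-arm and uncontrolled and includes age-related loss. Report β2 separately as the delayed arm's first-year change after its switch.
2. For spine and hip at week 96, estimate β1+β3 and label it the effect of switching 48 weeks earlier. Stop calling β3 the effect of switching at 96 weeks; relabelling β3 alone would not do, since it is not the week-96 difference. State that convergence of the arms is not evidence against a switch effect.
3. State in Section 11.1 that the between-arm adverse event comparison is read as TAF versus TDF for weeks 0-48 only, with weeks 48-96 reported separately.

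The cost is a text amendment and a few linear contrasts from a model and data already planned, with no extra visits, scans or participants. The limitation is that β2+β3 has no concurrent TDF control, so a small fall cannot be split into lost benefit and ageing.
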